#### **3.3.2 Primary Objective**

Are we able to see a decrease patient reported symptoms by 3 on the Rivermead post-concussion questionnaire or RPQ-3 and 10 on the RPQ-13 in those that receive targeted headache education in comparison to those who do not?

#### **3.3.3 Secondary Objectives**

##### **3.3.3.1 Key Secondary Objectives**

When and what type of health care services do participants in this study access, how frequently and is there a difference and between the two groups.

[figure not shown]
##### **3.3.3.2 Other Secondary Objectives**

- Does education through reinforcement of appropriate lifestyle and treatment strategies translate to similar pre-injury scores on the PART-0 tool at the 12-week time point.
- By the end of the study, the educational intervention group will be more satisfied in various aspects of their life as measured by the QUOLIBRI compared to their week 0 scores.

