**3.5.2.2 Summary of education by session: PowerPoint slides will be split into three distinct sections.**

*Initial session: (0 weeks): (In person)* We will outline the study. Approximately 30 minutes in duration.

[figure not shown]
- Review inclusion/exclusion criteria
- Explain study goals
- Obtain written/verbal informed consent
- We will cover topics such as defining the basic anatomy and the consequences of head trauma. We will include common symptoms along with when to seek medical guidance, medications to avoid and helpful lifestyle and treatment tips. Patients will be provided with links to approved websites.
- Prior to this session
  - Complete demographic information, medical history, trauma history and participant contact information (email or phone) will be gathered. If patients are identified in the ER, this information will be provided by the Triage nurse and forwarded to the research assistant who will be responsible for follow-up and providing the study materials.
  - Rivermead Post-Concussive Questionnaire (RPCSQ), PART-O and QOLIBRI (Yellow form: See Appendix) will be completed.
- *Second Session (6 weeks): (via email)*. Explain importance of keeping brain active; define the assessment of brain activity. 10-20 minutes to review the PowerPoint. Follow up will be done 1 week later either in person, email or via telephone to ensure patients are able to open the PowerPoint and have reviewed the literature. There will be no education or discussion about current treatment regimen or symptoms. Should a patient have questions regarding their current treatment plan or symptoms, our volunteers will put patients in contact with the Head Injury Nurse. All calls will be made during clinic hours in order to help facilitate communication with the clinic.

*Third Session (12 weeks)- (In person or sent via email)* We will explain importance of stress, sleep, and exercise on brain function, define the influence of lifestyle on recovery.

Approximate duration is 10-20 minutes. 1 week later follow up via telephone or email will occur by the methods listed above to ensure that the patient was able to open the PowerPoint. At this time we will:

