- Re-verify inclusion criteria to be done by Research Assistant. There will be no education or discussion about current treatment regimen or symptoms. Should a patient have questions regarding their current treatment plan or symptoms all calls will be made when the Head Injury Nurse is available to connect with patients directly.

- Rivermead Post-Concussive Questionnaire (RPCSQ), PART-O and QUOLIBRI will be completed via telephone or email and entered via REDCap into our database. Survey data will be uploaded by student or research assistant that is unaware of the patient's randomization.
- The patients who did not participate in the education seminar will fill out surveys at week 0 and 12.

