### **3.5.7 Recruitment**

Subjects will be recruited by individuals in the patient's circle of care including the emergency department triage nurse. Patients with mild traumatic brain injury will be enrolled at least 12 weeks after their injury. Recruitment of study participants fulfilling eligibility criteria will be identified and referred through the emergency room, their primary care physician or specialist to the St. Michael's head injury clinic in Toronto between January and December 2018.

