### **3.7 Methods: Data collection, management and analysis**

#### **3.7.1 Data Collection**

For all visits each patient will fill out a questionnaire (See Appendices for full surveys) using RedCap. If a patient is unable to enter the data using email directly, one of our research assistants will enter the data into the RedCap system via telephone interview. For the follow up survey if there is no response, we will attempt to contact the patient by phone three times. In regard to those patients seen in follow up in the clinic, we will ensure that they finish their follow up questionnaires after being seen by a healthcare professional to avoid unblinding. Patients' receiving the standard of care will be asked the same questions at week 0 and 12 with the same surveys as the education intervention arm of the study. A secure password protected master linking log will be able to house the patient name with study identification number.

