#### *Perceived Function in Society: Participation Assessment with Recombined Tools-Objective*

The Participation Assessment with Recombined Tools-Objective (PART-O) is an outcome scale measuring participation in the community. The PART-O consolidates questions from 3 commonly used instruments, and measures 3 domains of community participation post rehabilitation: Productivity, Out and About, and Social Relations; it is an objective measure of participation, representing functioning at the societal level. It asks questions like, *in a typical week, how many hours do you spend working for money, whether in a job or self-employed?* The PART-O was developed to examine long-term outcomes and can also be used to evaluate the effectiveness of interventions to improve social/societal functioning. The z-scores can be used to provide the basis for an assessment of progress in post-acute rehabilitation, allowing for an assessment of intra-individual differences in change across domains as well as inter-individual comparisons with the normative groups. When patients are using this tool, we will use this opportunity to ask about current employment status. We will use this tool in our study to assess to what degree do patients feel that they are able

to perform their activities of daily living. Along with how close do they believe they are to returning to premorbid level of functioning versus adjusting to their new health status.

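### The PART-O objective is set against pre-injury scores, which the protocol text does not say are collected, and it conflicts with the between-arm PART-O comparison in 3.5.5 and 3.7.7

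*Protocol*

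**What the plan says.** Section 3.3.3.2, repeated in the Protocol Summary, asks whether education will "translate to similar pre-injury scores on the PART-0 tool at the 12-week time point". It names no control group.

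Collection is described in three places:

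- Before the initial session (3.5.2.2), "Rivermead Post-Concussive Questionnaire (RPCSQ), PART-O and QOLIBRI (Yellow form: See Appendix) will be completed".
- At the third session, or at its follow-up contact one week later (3.5.2.2), "PART-O and QUOLIBRI will be completed via telephone or email and entered via REDCap into our database".
- For the control arm, 3.5.2.2 says: "The patients who did not participate in the education seminar will fill out surveys at week 0 and 12". Section 3.7.1 adds that standard-care patients "will be asked the same questions at week 0 and 12 with the same surveys as the education intervention arm of the study".

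On the time since injury, 3.5.7 states: "Patients with mild traumatic brain injury will be enrolled at least 12 weeks after their injury".

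Section 3.7.4 gives a sample PART-O item: "in a typical week, how many hours do you spend working for money, whether in a job or self-employed". It mentions z-scores that allow comparison with normative groups. It also says the tool will be used to learn how close patients believe they are to premorbid functioning. The appendix list (3.9) gives the baseline form as Rivermead, PART-O and QOLIBRI.

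Section 3.5.5 defines the PART-O outcome as a comparison with patients on standard care. Section 3.7.7 plans to compare PART-O scores between the two arms, with a one-way analysis for continuous variables and P<0.05.

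**The concern.** An objective fixes what has to be measured and what it is compared with. Here the comparator is a score from before the injury, and the described schedule starts well after it. A SAP can settle how to analyse a score, but it cannot supply one that was not collected, so this is not a detail that can be left to a later document.

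The second difficulty is that the protocol asks two different PART-O questions. The objective asks whether patients are back to their former level. The outcome and statistics sections ask whether the education arm differs from standard care. The answers can diverge: the arms may differ while both remain below their pre-injury level, or both may have returned to it with no difference between them. At the end of the trial it would be unclear which result answers the objective.

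**Working it through.** No formula for power or sample size applies, and the plan gives no figure for this objective to reproduce. The check is to place each stated PART-O assessment on the time-since-injury axis and look for one that refers to the time before injury.

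1. **Week 0.** Enrolment is at least 12 weeks after injury (3.5.7), so the week-0 PART-O falls at 12 weeks or later. This is the chronic phase as 3.2 defines it.
2. **Week 12.** 12 + 12 = at least 24 weeks after injury. If the form is completed at the follow-up contact one week after the third session (3.5.2.2), it is 12 + 12 + 1 = at least 25 weeks.
3. **Other visits.** Section 3.7.1 says "For all visits each patient will fill out a questionnaire", which might add a survey. Any such visit follows enrolment, so it is also post-injury.
4. **Reference period of the items.** The sample item in 3.7.4 asks in the present tense about a typical week. It is one example and does not settle the whole form, but nothing in the text sets a pre-injury reference period.
5. **Other references in 3.7.4.** The normative groups are an external standard, not a patient's own earlier score. The sentence on closeness to premorbid functioning concerns what patients believe and defines no pre-injury PART-O score.

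Stated PART-O assessments that refer to the time before injury: none.

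The contrasts that the stated data allow are then:

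| Contrast | Obtainable from the stated data? |
|---|---|
| Week 12 minus pre-injury (the objective) | No |
| Week 12 minus week 0, within arm | Yes |
| Education minus standard care at week 12 (3.5.5, 3.7.7) | Yes |
| Education minus standard care at week 12, adjusted for week 0 | Yes; both arms complete both surveys |

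The one contrast that the objective names is the one that cannot be formed.

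**The case against.** The strongest reply is that the questionnaires are not in the text at hand. Section 3.7.1 refers the reader to the appendices for the full surveys, and the appendix list is only one line per form. The sentence in 3.7.4 on premorbid functioning suggests that the authors had some pre-injury reference in mind. If the baseline form has a recalled pre-injury PART-O, the objective can be addressed, with recall error. This stands. The point is therefore limited to what the protocol text states: it would be too strong to say that no patient will have a pre-injury score or that the objective can never be answered.

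A reader might also infer that week 0 will stand in for the pre-injury score, so that patients who did not change would be counted as recovered. Nothing in the protocol says this, and the wording points the other way: the neighbouring QOLIBRI objective names the week-0 scores explicitly, so the authors appear to mean something else by pre-injury.

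A reader might further infer that a non-significant test will be taken as similarity, and size the problem by power. With 28 per arm, a two-sample t-test has 80% power at about 0.76 SD. That figure belongs to education versus standard care. A within-patient comparison of 28 would give about 0.55 SD of the change. Section 3.7.7 applies its tests to the between-arm comparison only, and no section equates non-significance with similarity. Neither figure measures this defect.

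Finally, the between-arm comparison is already planned and this is one of the other secondary objectives. That is so, and it limits the weight of the point, but the mismatch in wording remains.

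**Conclusion.** The point holds in limited form. As worded, the PART-O objective has no comparator in the data that the protocol text describes, and it asks a different question from 3.5.5 and 3.7.7. In size, none of the stated PART-O assessments carries a pre-injury reference, and the earliest falls at least 12 weeks after injury.

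This rests on two assumptions: that the baseline form contains no recalled pre-injury PART-O beyond what the text describes, and that pre-injury refers to patients' own earlier level, not to a norm. If the first is wrong, the text should say so, and *similar* would still need a definition.

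The primary outcome, the sample size and the randomised between-arm comparison are not affected. The correction should be made, but it does not put the trial's main result in doubt.

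**What to change.** - **Reword the objective** in the Protocol Summary and 3.3.3.2 as week-12 PART-O in the education arm compared with standard care, and remove the reference to similar pre-injury scores. This brings it into line with 3.5.5 and 3.7.7.
- **In 3.7.7**, replace the unadjusted one-way comparison for PART-O with one adjusted for week-0 PART-O, for example an analysis of covariance. The gain in precision depends on the correlation between the two scores, which the protocol does not give.
- **If return to the pre-injury level is truly wanted**, state in 3.5.2.2 and 3.7.1 that a recalled pre-injury PART-O is collected in both arms at week 0, acknowledge its recall error, and define *similar* by a margin set in advance. If the baseline form already includes such a version, say so.

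The first two changes cost only wording and use data that both arms already provide. The third, if the form does not yet exist, adds a few minutes per patient at week 0.

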### 3.4 Trial Design

This study is a blinded randomized control trial, which is the optimal trial design to determine whether a cause-effect relationship exists between our educational intervention and the current standard of care.

#### 3.4.1 Post Traumatic Headache Education Study Flow Diagram

**3.4.1.1 *Figure 1: Flow diagram of patient enrollment, allocation and follow up.***

## **3.5 Methods: Participants, Measures and Outcomes**

### **3.5.1 Eligibility Criteria**

#### **3.5.1.1 *Inclusion Criteria***

Inclusion criteria will be individuals between the age of 18- 65 years of age with a chronic mTBI based on CDC criteria. They must have the ability to give consent, speak English with awareness that they will need to be contacted at various time points, and must have access to email. We will include patients that score 3 or more on the RPQ either in the ER or during their initial assessment. They must be medically stable.

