Based on these studies, the question remains as to how best consistently treat this unique patient population. We know that many mTBI patients are not consistently being referred to a specialized clinic directly from the ER and of those patients they may present months later to their primary care providers, walk-in clinics or the ER after their symptoms persist. Our goal is to set in place a standard of care that will decrease symptom reporting and improve functional outcomes, starting with a patient population that is already being provided a multi-disciplinary care approach. Allowing the patient to experience improved self-efficacy with appropriate levels of expectations and perceived improvement in quality of life. We also hope to show that we can reduce the number of health care related visits (ER, Walk-in clinics etc.) that patients with post-traumatic headache will access in comparison to the current standard of care. Future goals will include using this approach to assess other post concussive symptoms in the multi-disciplinary clinic along with developing educational material that provides a clear and consistent message when treating head injury patients. We would also like to expand this education model to different clinic settings in order to provide this level of care to patients more acutely and ultimately reduce wait times for subspecialty clinics.

Grant 17-0098-GAP, REB 17 227

Version Date: April 16, 2019

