### **3.2 Aim of the Study**

The aim of the study is to ask the question as to whether or not targeted education will decrease symptom reporting in those suffering from post-traumatic headache after mild traumatic brain injury. The primary endpoints being measured include symptom reporting, perceived improvement in quality of life, utilization of health care services and return to baseline level of functioning.

This study will compare two groups of patients that are in the chronic phase (12 weeks and on) of their post-traumatic headache symptoms.

This model of educational intervention aims to change the way we deliver education material to this specific subset of patients. The goal is to apply this method of education to individuals with other mild-traumatic brain injury symptoms that can be realistically provided in a primary health care setting, ultimately reducing wait times for subspecialty clinics. Questions asked throughout the study will be provided by common data elements that will be used not only to standardize the study but to promote further research in the field across multiple sites in the province.

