### **3.5.3 Outcomes**

#### **3.5.4 Primary Outcome Measures**

Targeted education provided to patients suffering from post-traumatic headache will be assessed using the RPQ. The RPCSQ is a 16-question instrument that examines post-concussion symptoms rated by the patient according to the increase in their frequency compared with premorbid levels. The total score is calculated based on 2 domains (cognitive and emotional-somatic) and ranges from 0 to 72. The RPQ has been shown to measure severity of postconcussion symptoms reliably with good test-retest and inter-rater reliability for individual symptom scores. Based on previous studies, splitting the RPQ into two subscale scores: RPQ-3 uses the sum of scores from three items (headaches, dizziness and nausea) and RPQ-13 uses the sum of scores of the other 13 items. Higher scores especially for the RPQ-13 subscale are associated with greater impact on lifestyle. For our study significance will be observed if patients reported symptoms decreased by 3 on the RPQ-3 and 10 on the RPQ-13.

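### The inclusion criteria do not require the post-traumatic headache that the trial says it studies, and the RPQ entry score has no named scale and may predate enrolment by 12 weeks or more.

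*Protocol*

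**What the plan says.** Section 3.2 defines the population by headache: "This study will compare two groups of patients that are in the chronic phase (12 weeks and on) of their post-traumatic headache symptoms". Section 3.1 selects headache as the symptom to study and gives the ICHD-3 definition of post-traumatic headache, with onset within 7 days and the persistent form beyond 3 months. Section 3.7.3 says that headache symptom reporting will be compared between the arms.

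Section 3.5.1.1 admits "individuals between the age of 18- 65 years of age with a chronic mTBI based on CDC criteria" and then sets the symptom threshold: "We will include patients that score 3 or more on the RPQ either in the ER or during their initial assessment". The exclusions in 3.5.1.2 concern more severe brain injury, other neurological, psychiatric and substance use disorders, and circumstances that would prevent follow-up. Neither list mentions headache.

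On timing, 3.5.7 states: "Patients with mild traumatic brain injury will be enrolled at least 12 weeks after their injury". Section 3.5.2.2 has the RPQ completed before the first session, but attaches no entry threshold to that score.

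On the outcome, 3.5.4 says that "significance will be observed if patients reported symptoms decreased by 3 on the RPQ-3 and 10 on the RPQ-13". It defines the subscales as follows: "RPQ-3 uses the sum of scores from three items (headaches, dizziness and nausea) and RPQ-13 uses the sum of scores of the other 13 items".

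**The concern.** Eligibility is settled in the protocol itself, and here it selects a wider group than the aim describes. A patient with chronic mTBI, poor sleep and fatigue but no headache meets every written criterion. So does a patient whose qualifying score was recorded at an ER visit well before enrolment, whatever the week-0 questionnaire shows.

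Two things are at stake. The first is interpretation: a result from a mixed mTBI sample does not directly answer a question about headache education in post-traumatic headache. The second is sensitivity: patients who start low on RPQ-3 or RPQ-13 have little room to fall, so they narrow the difference the trial can show against its targets of 3 and 10. The problem does not bias one arm against the other, because both arms are drawn under the same criteria before allocation.

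**Working it through.** **Aim against criteria.**

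| Element | Aim and outcome (3.1, 3.2, 3.7.3) | Entry (3.5.1.1, 3.5.1.2, 3.5.7) |
|---|---|---|
| Condition | chronic post-traumatic headache | chronic mTBI |
| Headache | ICHD-3 definition given | not required |
| Symptom score | falls on RPQ-3 and RPQ-13 | 3 or more, scale not named |
| When scored | week 0 and week 12 | ER or initial assessment |

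Section 3.5.2.2 has the criteria reviewed at the first session. That review applies the same criteria, so an ER score still satisfies them. The second check, at the third session around week 12, comes too late to affect entry.

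**Age of the score.** Enrolment is at least 12 weeks after injury. If the ER score comes from the injury visit, its age at enrolment is at least 12 weeks. If the patient came to the ER later, it is younger. So the score can be 12 weeks or more old, but need not be.

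**Room to fall.** Each subscale is a sum of item scores and cannot go below zero.
- A fall of 3 on RPQ-3 needs a baseline RPQ-3 of at least 3.
- A fall of 10 on RPQ-13 needs a baseline RPQ-13 of at least 10.
- Both falls together need both conditions, so the total must be at least 3 + 10 = 13.

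The threshold of 3 then depends on the scale that is meant.
- If it is the total, a patient at 3 has RPQ-13 of at most 3 and cannot fall by 10. Any total from 3 to 12 rules out at least one of the two falls.
- If it is RPQ-3, a fall of 3 is just possible. RPQ-13 still has no minimum, and headache is still not needed because dizziness and nausea also count.

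On either reading, the criteria admit patients without headache and patients who cannot show one or both targeted falls.

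**Can this be turned into a power loss?** The attrition step reproduces: 28 / (1 − 0.20) = 35 per arm, and 56 / 0.80 = 70. The 28 itself comes from headache prevalence, 0.21 to 1.00 against 0.26, and that range does not fix one sample size. At two-sided 0.05 and 80% power, the pooled two-proportion formula gives 1128 per arm at 0.21 and 6 at 1.00. The midpoint 0.605 (an assumption) gives 29 with the unpooled formula:

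(1.960 + 0.842)² × (0.605 × 0.395 + 0.26 × 0.74) / (0.605 − 0.26)² = 28.5, rounded up.

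No RPQ change or RPQ standard deviation enters section 3.5.6. The protocol therefore has nothing from which to compute what low-scoring entrants cost.

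**The case against.** The strongest reply is that few such patients will appear. The population comes from a tertiary head injury clinic. Section 3.1 calls headache a consistently reported symptom, and the preliminary study it cites found persistently high RPQ scores at least 6 months after injury. Entry also requires chronic mTBI, which works against a fully recovered patient getting in. This stands, and it limits the likely size of the problem. It does not make the criteria agree with the aim.

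Other parts of the reply correct readings that a reader might infer.
- *Every ER score is at least 12 weeks old.* Section 3.1 says of these patients that "they may present months later to their primary care providers, walk-in clinics or the ER after their symptoms persist", so an ER score can be recent.
- *The patients without room are those with a total below 13.* A total below 13 does rule out achieving both falls, but so does RPQ-3 of 2 with RPQ-13 of 35, a total of 37. The conditions apply to each subscale.
- *A patient without headache is at the floor of RPQ-3.* That subscale also counts dizziness and nausea, and the sessions cover sleep, stress and exercise, which may act on RPQ-13.
- *Each patient must fall by 3 and 10.* Section 3.3.2 asks for a decrease compared with the other arm and 3.7.7 compares scores between arms. The protocol does not clearly set a per-patient responder rule. A low scorer can still improve and contribute, only by less.

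The flow diagram (3.4.1) and the headache assessment form listed in 3.9 are not shown and may bear on screening. The written criteria refer to neither.

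**Conclusion.** The mismatch is real and worth correcting. The aim names chronic post-traumatic headache. The criteria require only chronic mTBI and a score of 3 or more on an unnamed RPQ scale, which may have been taken 12 weeks or more before enrolment. Patients with no current headache, or with RPQ-3 below 3 or RPQ-13 below 10, can enter and reduce the achievable contrast against the targeted falls.

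No power loss can be attached to this trial. A reader might try. With 28 per arm, the effect detectable with 80% power is (1.960 + 0.842) × √(2/28) = 0.749 SD. If a share f of patients has no effect at all, power is Φ(2.802 × (1 − f) − 1.960), which gives 71%, 61% and 50% for f of 10%, 20% and 30%. These figures rest on an effect solved backwards from the sample size, on assumed shares, on an unchanged standard deviation, and on zero effect in patients who may still improve somewhat. The documents support none of these, so the figures illustrate a mechanism and do not estimate its size here.

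The conclusion itself rests only on the written criteria and on subscale scores having a minimum of zero.

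**What to change.** In 3.5.1.1:
- Require current post-traumatic headache as 3.1 defines it, shown by a headache item above zero on the week-0 RPQ, in both arms and before allocation. The item alone shows current headache; the definition in 3.1 supplies the link to the injury.
- Delete the option of using an ER score.
- Name the scale to which the threshold of 3 applies (total, RPQ-3 or other).
- If an RPQ-3 or RPQ-13 minimum is set, the sponsor should justify it against the targeted falls of 3 and 10. A minimum on RPQ-3 alone would leave RPQ-13 without one.

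The cost is a short rewrite of the eligibility text, using a questionnaire already completed at week 0. Some patients without headache would be screened out and recruitment may be slower, by an amount the documents do not allow to be estimated.

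This protocol version is dated April 2019 and recruitment was planned for 2018, so enrolment may already be complete. In that case, prespecify an analysis of patients with headache at week 0, and describe the enrolled population in reports as mTBI patients meeting the criteria actually applied. That subgroup is defined on a baseline item but will be smaller than the full sample, so its estimate will be less precise.
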